4.6.4 Sensitivity Analyses

4.6.4.1 Analysis Using Hypothetical Strategy for COVID-19 Intercurrent Events

The analysis of the primary efficacy endpoint will be repeated in the ITT population, applying the hypothetical strategy for COVID-19 intercurrent event. This will exclude any mRS data collected after being infected with COVID-19. Missing Day 90 mRS scores, including those being excluded due to COVID-19 intercurrent event, will be imputed according to the methodology described in Section 4.9.1.1. In case of non-existence of post-baseline mRS data after applying the hypothetical strategy, subject(s) will be

excluded from the analysis. In this analysis, treatment policy strategy will still be used for non-COVID-19 intercurrent event.

4.6.4.2 Per Protocol Analysis

The analysis of the primary efficacy endpoint will be conducted in the PP population. This analysis will be based on the mRS data at Day 90 with the LOCF imputation.

4.6.4.3 Tipping Point Analysis

To assess robustness of the primary efficacy analysis result, a tipping point analysis will be conducted. In this analysis, multiple imputation (see Section 4.9.1.2 for details) will be employed to impute the missing mRS scores at Day 90.

In these imputations, the log-odds for a favorable outcome ($mRS \leq k$) will be penalized in the TNK treatment group via an additional term Δ (see Tang 2018). Thus, $\exp(-\Delta)$ is the additional term in the odds ratio of a favorable outcome between the TNK and Placebo groups under various assumptions of missing data mechanism, where $\Delta=0$ corresponds to missing at random (MAR) and $\Delta>0$ denotes missing not at random (MNAR). The value of Δ will be gradually increased until the p-value crosses the pre-specified nominal alpha level (0.003 at interim, 0.049 at final analysis).

Rubin's standard error will be used in the normal approximation formula to construct confidence intervals and p-values (Little et al. 2002). If the p-value does not reach the nominal alpha level within a reasonable range of data, then it will be concluded that the finding about the treatment difference is sufficiently robust to violations of the MAR assumption. If the p-value exceeds the nominal alpha level for some value of Δ , then a plot of p-values versus Δ will be provided. A monotone smoother will be added to the plot to help locate the tipping point.

4.6.5 Subgroup Analyses

In addition to the exploratory subgroup analyses specified in Section 4.6.3.1, the primary efficacy endpoint will also be analyzed on the following subgroups:

- Age: <80 vs ≥ 80 years
- Baseline NIHSS: ≤ 15 vs > 15
- Baseline infarct volume: <20 mL, ≥ 20 mL and <50 mL, ≥ 50 mL
- Time (in hours) between stroke onset to randomization: <16 hours vs ≥ 16 hours
- Baseline occlusion type: ICA vs M1 vs M2
- Protocol version: Protocol V1-4 vs Protocol V5
- Mechanical thrombectomy planned at baseline: Yes vs No
- Mechanical thrombectomy performed (defined as successful clot manipulation): Yes vs No

- Time (in minutes) between study drug administration and groin puncture: groups defined by tertiles of the time variable. The analysis will include all patients who had groin puncture performed regardless of final performance of mechanical thrombectomy.

These subgroup analyses will be conducted using the same imputations and analysis methodology as the primary efficacy analysis (see Section 4.6.1), but proportionality of odds will not be re-evaluated for each subgroup.

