6.1 DETERMINATION OF SAMPLE SIZE

The purpose of this study is to demonstrate superiority of tenecteplase over placebo, when administered between 4.5 to 24 hours of last-known well time, in patients who have a vessel occlusion and evidence of salvageable tissue on their baseline CTP or MRI. The primary efficacy endpoint is the mRS score at Day 90. The distribution of the ordinal mRS scores will be compared between the two treatment groups.

Approximately 456 patients will be enrolled in this study. Assuming the distribution of mRS scores at Day 90 in the two treatment arms as shown in Table 7 and a 5% dropout rate in the study, approximately 228 patients in each treatment group will provide at least 90% power to detect the specified difference in the distribution of the mRS scores at the 2-sided 0.049 significance level (after adjustment for one interim efficacy analysis; see Section 6.6). This calculation is based on the East® 6.4.1 software. This corresponds to being able to detect a common odds ratio of at least 1.76 (tenecteplase vs. placebo),

with a total sample size of approximately 432 evaluable patients, assuming a 5% dropout rate.

Table 7 Assumed Distribution of 90-Day mRS in Sample Size Determination

mRS	0	1	2	3	4	5	6
Tenecteplase (% of patients)	17	20	16	15	13	7	12
Placebo (% of patients)	13	13	12	14	18	12	18

mRS=modified Rankin Scale.

The sample size estimation is highly dependent on the distribution assumption of 90-day ordinal mRS score for both treatment arms; thus, additional power calculation is provided with 456 total patients for different distribution scenarios on the mRS at Day 90. As shown in [Table 8](#), compared with the assumption used in current sample size calculation ([Table 7](#)), Scenario 1 (from the DEFUSE 3 trial) assumes a more optimistic outcome in the tenecteplase treatment arm than the placebo arm, while Scenario 2 (from the EXTEND-IA-TNK trial) assumes less treatment difference between the two treatment arms. The resulting power for both scenarios are shown in [Table 9](#).

Table 8 Distribution of 90-Day mRS from Different Scenarios

	Scenario 1						
	Tenecteplase (% of patients)	10	16	18	15	18	8
Placebo (% of patients)	8	4	4	16	27	16	26
Scenario 2							
Tenecteplase (% of patients)	28	21	14	14	8	6	10
Placebo (% of patients)	18	23	9	12	14	7	18

mRS=modified Rankin Scale.

Table 9 Power Consideration by 90-Day mRS Distribution Scenarios

mRS distribution assumption	Evaluable Sample size	Type I Error	Power

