4.6.3.7 Planned Thrombectomy Not Performed

A planned thrombectomy may not be performed in some cases. This includes patients with partial or complete recanalization of the qualifying vessel occlusion who did not go to angiography suite because non-invasive imaging demonstrated recanalization, or patients who have undergone catheter angiography and are found to no longer to have an occlusion of the qualifying vessel.

The proportion of patients where a planned thrombectomy was not performed due to partial or complete recanalization will be summarized by treatment group and analyzed using logistic regression adjusted as specified in Section 4.6 but excluding the planned thrombectomy variable. Observed counts and percentages for tenecteplase and placebo arms, and model based odds ratio, corresponding Wald 95% CI and p-value will be produced.

4.6.3.8 Overall Survival at Day 90

Cumulative incidence of all deaths will be presented by means of Kaplan-Meier plots if there are sufficient events (at least 5 in each treatment group). Time to death since randomization will be analyzed with a stratified log-rank test using variables as specified in Section 4.6. Death occurred up to Day 90 visit (or within 120 days since randomization, which is the study day cut-off for efficacy outcome evaluation) will be included in the analysis. Patients who did not die up to Day 90 visit will be censored at the last study assessment date. In addition, death occurred after Day 90 visit and the relatedness of death is determined by having a related fatal AE will also be included in the analysis.

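### The thrombectomy-performed subgroup is fixed after randomisation and may itself respond to tenecteplase, so its treatment odds ratios can mislead; the planned-at-baseline subgroup should carry the estimate

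*SAP*

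**What the plan says.** SAP 4.6.5 lists further subgroups for the primary endpoint. Most are baseline variables, including thrombectomy planned at baseline (Yes/No). Two are not:

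- "Mechanical thrombectomy performed (defined as successful clot manipulation): Yes vs No".
- Tertiles of the time from study drug to groin puncture. For these, "The analysis will include all patients who had groin puncture performed regardless of final performance of mechanical thrombectomy".

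All are run with the imputations and methods of the primary analysis. Under SAP 4.6.1 that means an odds ratio with a confidence interval and, for the proportional odds model, a Wald p-value. SAP 4.6 says all efficacy analyses are evaluated for superiority. SAP 4.6.5 does not distinguish the two post-randomisation variables from the rest.

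Elsewhere the documents treat non-performance of thrombectomy as something treatment may influence:

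- SAP 4.6.3.7 compares between arms, as an exploratory efficacy endpoint, "The proportion of patients where a planned thrombectomy was not performed due to partial or complete recanalization".
- SAP 4.6 classes planned-but-not-performed thrombectomy as an intercurrent event, handled by treatment policy.
- Protocol 1.3 says better intravenous thrombolysis may raise early reperfusion before thrombectomy and may reduce the need for the procedure.

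**The concern.** Randomisation makes the arms comparable within groups defined before treatment. It does not do so within groups defined by something treatment can change. Suppose tenecteplase opens some vessels early, so that thrombectomy is no longer needed. Those patients fall in the No group on tenecteplase, while their counterparts on placebo fall in the Yes group. If such patients tend to do well, the tenecteplase No group gains good-prognosis patients and the tenecteplase Yes group loses them.

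The expected artefact is apparent benefit without thrombectomy and apparent harm, or reduced benefit, with it. Whether lysis helps patients who do or do not go on to thrombectomy is a practical question this trial raises, so such a pattern could easily be taken at face value. A larger sample would not shrink it.

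**Working it through.** **1. The plan's own figure.** The documents give no figure for these subgroups, so the check starts from the sample size in Protocol 6.1. The inputs are the "2-sided 0.049 significance level", "a total sample size of approximately 432 evaluable patients, assuming a 5% dropout rate", and the mRS distributions in Table 7 (Table 1 in the SAP), in percent for scores 0–6:

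- tenecteplase 17/20/16/15/13/7/12
- placebo 13/13/12/14/18/12/18

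The common odds ratio fitted to these by maximum likelihood is 1.74, against the stated 1.76. Whitehead's formula gives V = N(1 − Σp̄³)/12 = 432 × (1 − 0.0216)/12 = 35.22. Power is Φ(√35.22 × ln 1.744 − 1.969) = Φ(3.301 − 1.969) = 90.9%. A simulated tie-corrected Wilcoxon-Mann-Whitney test with 216 per arm gives 90.6%. The stated power of at least 90% reproduces, so Table 7 is a sound base for what follows.

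**2. Illustration with no drug effect on any patient's mRS.** These assumptions are not in the documents:

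- 30% have no thrombectomy in either arm.
- A further fraction e (5% or 12%) recanalizes early on tenecteplase only.
- Those patients have prognostic odds ratio R (2 or 3) for a better mRS.
- Everyone else follows the Table 7 placebo column, P. The shifted distribution is G.

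The group mixtures are:

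- No: tenecteplase (0.30·P + e·G)/(0.30 + e); placebo P.
- Yes: tenecteplase P; placebo ((0.70 − e)·P + e·G)/0.70.

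Take e = 12% and R = 3, and look at mRS 0–2. Under P this is 38%. Under G the odds are 3 × 0.38/0.62 = 1.839, which is 64.8%.

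- No: tenecteplase (0.30 × 38 + 0.12 × 64.8)/0.42 = 45.6%; placebo 38%.
- Yes: tenecteplase 38%; placebo (0.58 × 38 + 0.12 × 64.8)/0.70 = 42.6%.

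Fitting the common odds ratio to the full seven-level distributions (above 1 favours tenecteplase; truth 1.00):

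| Extra recanalization e | Prognostic OR R | No | Yes |
|---|---|---|---|
| 5% | 2 | 1.10 | 0.95 |
| 5% | 3 | 1.16 | 0.93 |
| 12% | 2 | 1.21 | 0.89 |
| 12% | 3 | 1.35 | 0.83 |
| 0% | any | 1.00 | 1.00 |
| any | 1 | 1.00 | 1.00 |

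**3. A second model, with recanalization in both arms.** Patients are always-recanalizers, recanalizers on drug only, or never-recanalizers, and again no patient's mRS depends on the drug. Assumptions: 60–80% have planned thrombectomy, 10% of attempted procedures fail, and R is 2–4. The 10% vs 22% row borrows the reperfusion rates in Protocol Table 2. Those come from a trial of tenecteplase against alteplase within 4.5 hours and are illustrative only.

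| Early recanalization, placebo vs tenecteplase | Performed | Not performed |
|---|---|---|
| 10% vs 10% | 1.00 | 1.00 |
| 5% vs 10% | 0.93–0.97 | 1.03–1.12 |
| 10% vs 22% | 0.84–0.91 | 1.07–1.21 |
| 5% vs 20% | 0.82–0.90 | 1.09–1.32 |

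The all-patient odds ratio is 1.00 in every row. With 80% planned and 228 per arm, simulated false-positive rates at a nominal 4.9% (performed / not performed) are:

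- 7.0% / 6.4% for 10% vs 22% with R = 2
- 12.7% / 10.7% for 10% vs 22% with R = 4
- 16.0% / 16.8% for 5% vs 20% with R = 4
- 5.2% / 4.7% for 10% vs 10%

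**4. Limits.** Both models are unadjusted. The planned covariates would remove only the part of the prognostic difference that they explain. The drug-to-groin tertiles were not modelled.

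**The case against.** The strongest case on the other side has four parts.

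- **The drug effect on thrombectomy is a hypothesis.** SAP 4.6.3.7 specifies a two-arm comparison with an unknown result, and Protocol 1.3 speaks only of potential reductions. This stands, and the conclusion is conditional on it.
- **The inputs are assumed and the bias may be small.** At 5% vs 10% recanalization the odds ratios stay within 0.93–1.12. Even at the extreme of step 2, with 216 evaluable per arm, approximate 95% intervals are 0.77–2.36 (No: 91 vs 65 patients) and 0.55–1.26 (Yes: 125 vs 151), so a typical result would be inconclusive. False-positive rates above 10% appear only with a prognostic odds ratio of 4. This stands as a limit on size. It does not remove the bias.
- **Little depends on these analyses.** They lie outside the primary analysis and the testing order in SAP Table 3, and the baseline counterpart is already planned. This stands.
- **A descriptive table by arm shows the same selected comparison, so a label alone would do.** This is partly right, and the label is essential. Dropping the odds ratio and p-value also avoids presenting the comparison as a treatment-effect estimate.

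A reader might go on to infer that tenecteplase changes the drug-to-groin time. No section says so. What the documents support is that some recanalized patients never reach the angiography suite (SAP 4.6.3.7), so entry to the punctured set may depend on the drug. Keeping every punctured patient, including those found open at angiography, limits that selection.

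**Conclusion.** The point holds in conditional form. Thrombectomy performed is a post-randomisation variable that the documents expect treatment may alter, and SAP 4.6.5 plans treatment-effect odds ratios within it without a caveat. If tenecteplase increases early recanalization and recanalizers have a better prognosis, those odds ratios are biased in opposite directions even with no effect on Day 90 mRS. The illustrative size is 1.10–1.35 in the No group and 0.83–0.95 in the Yes group, on the assumptions of step 2.

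Two stronger readings are tempting and are not supported:

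- **That the estimates are biased even if the drug does nothing at all.** Subgroup membership is then independent of arm and both odds ratios are 1.00. They are also 1.00 if recanalization is unrelated to prognosis.
- **That early recanalizers enter the No group only on tenecteplase.** SAP 4.6.3.7 compares this outcome in both arms. The bias needs only a higher rate on tenecteplase.

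The drug-to-groin tertiles carry a weaker, unquantified version, through entry to the punctured set. The impact is confined to exploratory results. The primary analysis, its type I error and its power are unaffected. This is a desirable improvement, not a serious defect.

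**What to change.** In SAP 4.6.5:

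- Take treatment-effect estimates on this question from thrombectomy planned at baseline (Yes/No), which is already listed. Its membership cannot depend on the arm, so the models above give 1.00 there in every scenario.
- Report thrombectomy performed and, as a precaution, the drug-to-groin tertiles as descriptive mRS tables by arm, with no odds ratio or p-value.
- Label both as defined after randomisation and not to be read causally.

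The cost is a few lines of SAP wording, and fewer models are run. The downside is that there would be no model-based estimate in a subgroup that clinicians may ask about.

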Patients will undergo two follow-up MRI scans. Patients who cannot undergo an MRI will undergo a multimodal CT at the first follow-up and a non-contrast CT at the second follow-up. The first follow-up scan will be obtained at approximately 24 hours (± 6 hours)

[figure not shown]
after randomization and will include an assessment of recanalization and reperfusion, per standard of care. The second MRI will be obtained between 72 to 96 hours after randomization for assessment of final infarct volumes.

All patients will be evaluated using mRS at discharge/Day 5, Day 30, and Day 90 after randomization for clinical outcome evaluation.

The primary analysis is to compare the efficacy of tenecteplase versus placebo in all patients at Day 90, as assessed by the mRS score with an ordinal analysis. As a key prespecified subgroup analysis, the trial will also assess the effect of tenecteplase separately in patients with ICA/M1 and in patients with M2 occlusions.

[Figure 1](#) presents an overview of the study design. A schedule of activities is provided in [Appendix 1](#).

Figure 1 Study Schema

hr=hour; MT=mechanical thrombectomy; PBO=placebo; R=randomized; TNK=tenecteplase.

Note: The primary endpoint will be assessed at the Day 90 visit.

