4.6.3 Exploratory Efficacy Endpoints

4.6.3.1 Subgroup Analyses for the Primary Endpoint

The primary efficacy endpoint, mRS score at Day 90, will be analyzed by the following subgroups: (1) Occlusion type (ICA/M1 or M2 occlusions) and (2) Randomization site (ECC or nECC). These subgroup analyses will be conducted using the same imputations and analysis methodology as the primary endpoint (see Section 4.6.1), however there will be no adjustment by the variable defining the subgroup. Proportionality of odds will not be re-evaluated for each subgroup. mRS score at Day 30 will be analyzed in a similar manner for the randomization site subgroups (ECC or nECC). Additional subgroup analyses for the primary efficacy endpoint are described in Section 4.6.5.

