- (2) Discard all C_i where $S_i \leq 1\%$ of subjects in the full ITT set (i.e., the same cell size threshold is used for all ITT analyses and subgroup analyses).
- (3) Among the remaining C_i , prioritize the highest L_i and discard the rest. For example, if both (V1, V2, V5) and (V1, V3, V4, V5) have all cells $> 1\%$, (V1, V2, V5) will not be considered because it does not have the highest number of variables possible.
- (4) Among the remaining C_i choose the one with the highest S_i .
- (5) Among the remaining C_i (which have ties of both L_i and S_i), prioritize the C_i that contains V1, then V2, etc, until only one choice remains.

Signature Page for Statistical Analysis Plan - ML40787, V5 - Published
System identifier: RIM-CLIN-474627

Approval Task	[REDACTED]
	Company Signatory 29-Mar-2023 22:03:03 GMT+0000

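### The subgroup analyses, including the key ICA/M1 and M2 split, plan no estimate or test of whether the treatment effect differs between subgroups

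*SAP*

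**What the plan says.** Protocol 3.1 and the synopsis give the split by occlusion type a special status, calling it prespecified and key. They state: "the trial will also assess the effect of tenecteplase separately in patients with ICA/M1 and in patients with M2 occlusions". Protocol 6.4.3 compares the arms within each subgroup by a proportional odds model.

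SAP 4.6.3.1 covers occlusion type (ICA/M1 or M2) and randomization site: "These subgroup analyses will be conducted using the same imputations and analysis methodology as the primary endpoint". It drops the variable that defines the subgroup from the adjustment, which implies one model per level. SAP 4.6.5 adds nine further factors, among them a three-level ICA, M1, M2 split, with the matching sentence: "These subgroup analyses will be conducted using the same imputations and analysis methodology as the primary efficacy analysis". Under SAP 4.6.1 the proportional odds analysis yields a common OR, a Wald p-value and a 95% CI.

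SAP Appendix 5 selects the adjusting variables on the dataset being analysed. It notes that "the same cell size threshold is used for all ITT analyses and subgroup analyses", the threshold being 1% of the full ITT set.

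Neither document mentions a treatment-by-subgroup interaction, a heterogeneity test or a ratio of ORs.

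**The concern.** Per protocol 3.1, M2 patients generally do not go on to endovascular therapy, whereas ICA/M1 patients do if they meet guideline criteria. Once both results are reported, readers will ask whether tenecteplase works differently in the two settings. The planned output does not address that. It gives two p-values whose sizes depend heavily on how many patients each group contains.

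A significant result in the larger group beside a non-significant one in the smaller is easily read as a differential effect. If that pattern is common when the effect is identical, the key subgroup analysis invites a false conclusion about which patients benefit.

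**Working it through.** **Inputs from the documents.** Protocol 6.1: "approximately 228 patients in each treatment group will provide at least 90% power to detect the specified difference", at "the 2-sided 0.049 significance level"; common OR 1.76; 432 evaluable patients; the Table 7 mRS distributions. Allocation is 1:1 (protocol 4.2.1).

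**Assumptions not in the documents.** The M2 share is 10% to 50%, with 20% to 30% as the main range. Subgroup tests are two-sided at 0.05. The same true OR holds in both groups.

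**1. Reproduce the plan's power.** From Table 7, P(tenecteplase better) + 0.5 P(tie) = 0.5896. The tie-corrected Wilcoxon-Mann-Whitney approximation with 216 per arm at 0.049 gives 90.2% power, which agrees with the plan's figure of at least 90%. As a cross-check under proportional odds, var(log OR) = 12 / [n(1 − Σp̄³)], where p̄ is the mean of the two arms in each category. Here Σp̄³ = 0.0216, so at n = 432 the SE is √(12 / (432 × 0.9784)) = 0.1685. With log 1.76 = 0.5653, z = 3.355 and power is 91.7%.

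**2. Apply the same formula within subgroups.** At an M2 share of 20%:
- ICA/M1: n = 345.6, SE 0.188, z = 3.00, power 85.1%.
- M2: n = 86.4, SE 0.377, z = 1.50, power 32.3%.
- Exactly one significant: 0.851 × 0.677 + 0.149 × 0.323 = 0.576 + 0.048 = 62.4%.

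| M2 share | Power ICA/M1 | Power M2 | Exactly one significant | ICA/M1 only | ORs differ at least 1.5-fold |
|---|---|---|---|---|---|
| 10% | 89% | 19% | 74.5% | 72% | 47% |
| 20% | 85% | 32% | 62% | 58% | 34% |
| 30% | 80% | 45% | 53% | 44% | 27% |
| 50% | 66% | 66% | 45% | 22% | 23% |

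With a smaller common OR of 1.4, exactly one group is significant in 41% to 48% of trials. For a three-way ICA/M1/M2 split of 15/65/20% (15% is the protocol's ICA cap; the rest is assumed) at OR 1.76, significance is mixed in 82%.

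**3. The alternative.** In simulated trials with OR 1.76 in both groups (1,500 per setting), one pooled proportional odds model with a treatment-by-occlusion term declared a difference in 4.3% to 4.8%.

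**4. Power of that test.** The SE of the log ratio of ORs is √(SE₁² + SE₂²). At a 20% share it is √(0.0355 + 0.1420) = 0.421, so 80% power needs a ratio of exp(2.80 × 0.421), about 3.25. At 30% the SE is 0.368 and the ratio is about 2.8.

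**5. How much do differing covariates add?** Each Appendix 5 cell must exceed 1% of 456 = 4.56, so it needs at least 5 patients. In an occlusion subgroup four candidates remain besides protocol version. Crossed with treatment they form 2⁵ = 32 cells, needing at least 160 patients, or 35% of 456. A smaller M2 group cannot keep all four; ICA/M1 could if its cells are balanced. In simulation, omitting two prognostic covariates (assumed OR 2.5 each) in M2 only moved the median M2 OR from about 1.8 to 1.7 and added about 2 percentage points to the share with exactly one significant.

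**6. Number of tests.** SAP 4.6.3.1 has 4 within-level Day 90 comparisons and 4.6.5 has 21, so 25 in all. M2 appears in both lists, leaving 24 distinct. Five are defined after randomization: two for thrombectomy performed and three for tertiles of time from drug to groin puncture.

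**The case against.** The analyses are exploratory and outside the SAP Table 3 hierarchy. The protocol's stated aim is to assess the effect separately in each group, and separate estimates serve that aim. The SAP nowhere tells anyone to conclude a difference from one significant and one non-significant p-value. Because the two occlusion groups do not overlap, a reader could compute a heterogeneity z-test from the reported ORs and CIs, so the information is not lost. A formal interaction test would detect only large differences.

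Much of this stands. A reader might infer that the plan inflates the trial's type I error; it does not, since no subgroup result feeds the primary or secondary claims. A reader might also infer that covariate sets chosen separately, with the non-collapsibility of odds ratios, manufacture subgroup differences. Step 5 shows that this is a minor effect. Moreover, re-running Appendix 5 in each subgroup level is a reasonable inference from its text, not a stated step.

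What the objection does not remove is the omission. A comparison left for readers to reconstruct is not prespecified. An analysis labelled key will be interpreted, and low power argues for reporting the ratio of ORs with its CI, not for leaving it out.

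**Conclusion.** The concern holds as a gap in prespecified comparison and reporting, and it should be corrected. With an identical effect of the size the trial is designed to detect, the two occlusion groups would disagree on significance in about 53% to 62% of trials at M2 shares of 30% to 20%, against about 5% false calls from an interaction test. Subgroup size and chance account for most of this.

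The exact percentages rest on the assumed M2 share, the 0.05 subgroup level and a common OR of 1.76. The conclusion survives the wider range: 45% to 74.5% for shares from 50% to 10%.

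It should not be read as a finding that the subgroup estimates are biased, or that an interaction term would make them look alike. The estimates would still vary; the plan would gain a valid basis for judging the variation.

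**What to change.** In SAP 4.6.3.1 and 4.6.5:

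- For each baseline subgroup factor, fit one proportional odds model in the full ITT set with treatment, the factor, their interaction (two terms for a three-level factor) and the primary-analysis covariates. Include the factor as a main effect even if Appendix 5 has removed it. Do not re-select covariates within subgroups.
- Report the subgroup ORs with CIs from that model, and the ratio of ORs with its CI and the interaction p-value.
- State that no subgroup claim rests on within-subgroup p-values.
- If the primary method becomes the stratified WMW GenOR, compare the subgroup log GenORs, using the Appendix 4 variances, by a z-test for two levels or a chi-square test for three.
- Label thrombectomy performed and the drug-to-groin-puncture tertiles as descriptive only, because they are defined after randomization.
- State that the interaction test has low power: 80% needs a ratio of ORs of about 2.8 to 3.25 at M2 shares of 30% to 20%.

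The cost is SAP wording, one or two model terms per factor and a short extra programming step for the GenOR branch. The design, data collection and primary analysis do not change.
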